All study staff are HIPAA and CITI certified and will be trained in the use of the web-based platform. Additionally, all clinical staff conducting telehealth sessions will be oriented to the semi-structured curriculum, and the study coordinator who will also be conducting the intersession coaching will be trained and mentored by a CHLA researcher who has recently conducted a similar study utilizing a cell-phone based app and brief coaching for treatment of adolescents with obesity.

Subject Selection and Withdrawal

Inclusion Criteria

Prospective Group:

Youth age 14-18 who meet criteria for or are currently enrolled in the Empower weight management clinic will be included. These criteria include body mass index (kg/m2) that is either greater than the 99th percentile, or greater than the 95th percentile accompanied by an obesity-related comorbid condition such as hyperlipidemia, pre-diabetes or diabetes, non-alcoholic fatty liver disease (NAFLD), obstructive sleep apnea, or polycystic ovarian syndrome.

Youth will need to speak English but those whose parents' primary language is Spanish will be included.

Retrospective Control Group:

All eligible youth from our EMPOWER clinic patients whose first clinic visit occurred between January 2015 and June 30, 2019, and were 14-18 years old, were included in our control group.

Exclusion Criteria

Prospective Group: (1) significant intellectual or neurodevelopmental disability, ie previous diagnosis of autism spectrum disorder or developmental delay (2) non-English speaking; (3) age < 14 years and > 18 years (4) weight greater than 255 kg.

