• There is a small risk that people who are not connected with this study will learn a participant's identity or their personal information.

- Venipuncture risks include mild discomfort (or pain), bruising and swelling around the puncture site, dizziness or fainting, or infection (rare).
- Improvement in some or all of participants' symptoms
- The advancement of knowledge
- A new treatment or therapy for the condition under study

Early Withdrawal of Subjects

 They will not be punished or denied something which they would normally receive (e.g., threatening to withdraw health services to which an individual would otherwise be entitled) if they choose not to participate in this research or choose to withdraw early from participation.

Study Procedures

Screening for Eligibility

Script to be used by study staff and email to be sent to CHLA Health Network pediatrician offices.

Schedule of Measurements

The intervention telehealth group participants will have their anthropometric measurements and vital signs recorded onto their Case Report Forms (CRFs) during their in-person baseline, 3-month, and 6-month visits. Baseline lab reports that have been obtained by primary care providers included in Empower referral packets, if applicable, will also be recorded onto the CRF, as will follow-up lab work obtained at the 6 month inperson visit. If no baseline labs have been collected in the last 6 months by referring PMD, we will collect baseline bloodwork here at the CHLA CTU.

Intervention Visits

- (1) Group telehealth sessions twice per month for 6 months. The group sessions will be 60 minutes and involve delivery of a semi-structured curriculum including topics such as nutrition education, reducing barriers to physical activity, and how to celebrate with family and friends in a healthful manner, and will use interactive activities such as photovoice (see attached curriculum). Sessions will be facilitated by EMPOWER providers (physicians, psychologists, RDs, and PTs) who will use a combination of: (1) motivational interviewing techniques, modified for the group setting, (2) supportive exploration of barriers to behavior change and (3) setting SMART goals. Beginning with cohort 2, sessions will be recorded for internal use.
- (2) Brief individualized coaching by the research team between sessions, via telephone or email. It will be comparable to the personalized feedback and motivation provided in standard EMPOWER.

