 - 5.A1C, fasting glucose, fasting lipids, AST and ALT will be drawn at 6-month visit, and results will be documented as well. They will also be drawn at baseline, if participants did not have them performed as part of their clinical care during the previous 6 months. Baseline lab results will also be documented.

6.General session information for bi-weekly (every 2 weeks) telehealth sessions will be collected onto the Telehealth Session Report forms by the session facilitators, including which participants attended and how the facilitator felt the session went.

 Experimental procedures for Control Group subjects will be limited to data abstraction from the CHLA KIDS electronic medical record (EMR

Statistical Plan

As noted previously, the target recruitment of 32 intervention and 176 control was arrived at based on practicality and feasibility for a pilot study. For evaluation of changes in the continuous outcomes, BMI, blood pressure, and hemoglobin A1C, triglyceride level, and ALT, assessed at baseline and immediately following the end of the 6 month intervention, we will utilize regression methods, which will allow us to compare the magnitude of change between the telehealth intervention and the comparison group, taking into account both change from baseline to follow-up time points as well as relevant baseline covariates. For these analyses covariates will be participants' age, gender, and presence of existing medical conditions (e.g. diabetes; rheumatologic conditions) that could affect weight loss.

Update June 2021: Matched control group subjects will be identified by calculating a propensity score, by collecting data for all potential control patients seen in EMPOWER clinic in the approved date ranges. There is no change to the nature of the data points, and their data will be extracted from KIDS and entered into REDCap database as already outlined.

Update Dec 2022: Given the limited data available for each of the matched clinic control patients (many had missing lab and other values), it was determined that we should remove the "matched" inclusion criteria and collect data on all 176 eligible control patients, in order to have a statistically meaningful cohort.

Data Handling and Record Keeping

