Physical data will be stored in a locked office, locked storage unit, restricted access to authorized study personnel. Electronic data will be accessed through a secure computer/laptop, individual ID plus password protection, network restrictions, security software, and access terminated when authorized personnel leaves the study.

Any audio/video recordings will not be anonymized or de-identified because they will only be used by the study staff. The recordings will be deleted at the end of the study.

Study Monitoring, Auditing, and Inspecting

Direct identifiers and/or the key to the codes will be destroyed upon completion of the research (all data/specimens will be stripped of identifying information and/or the key to codes destroyed, paper documents shredded, electronic files purged, electronic media securely erased).

Study Administration

Funding source

All costs of the research will be paid for by the sponsor/funder. The study does not include standard of care procedures; however, costs of parent or participant time off from work, transportation, parking, babysitter fees, food purchased while at the hospital, etc. will not be paid for by the study.

For participants who have not had Hemoglobin A1C, fasting glucose, AST, ALT, and fasting

lipid panel within 6 months of the start of participation, cost of phlebotomy and lab processing will be covered by CTSI voucher awarded in support of this study.

Subject Stipends or Payments

Subjects from the telehealth intervention arm will be compensated with gift cards in the amount of \$10 for completion of questionnaires at the 3-month visit and \$20 at the 6-month visit. Gift cards will be given directly to the participants, whether they are minor age teens or adults.

Publication Plan

Dissemination of findings will include sharing information in local conferences. After complete data analysis, manuscription will be submitted for publication in a pediatric weight management, or pediatric nutrition journal.

Attachments

Informed Consent Documents (separate pages)
Questionnaires or Surveys (separate pages)

References

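### Telehealth baseline labs may be up to 6 months old at the start, so the A1C, triglyceride and ALT changes span 6 to 12 months and can include pre-treatment time

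*Combined protocol and SAP*

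**What the plan says.** Three places in the combined protocol and SAP accept an existing laboratory result as the telehealth baseline if it is at most 6 months old.

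- Study Procedures, Schedule of Measurements: "If no baseline labs have been collected in the last 6 months by referring PMD, we will collect baseline bloodwork here at the CHLA CTU".
- The list of data collected for the telehealth group, item 5: "They will also be drawn at baseline, if participants did not have them performed as part of their clinical care during the previous 6 months".
- Study Administration, Funding source: the study pays for baseline phlebotomy only where a participant lacks the named tests, including a "lipid panel within 6 months of the start of participation".

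Follow-up timing is fixed by item 5 of the same list: "A1C, fasting glucose, fasting lipids, AST and ALT will be drawn at 6-month visit". No visit window is given.

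The Statistical Plan analyses A1C, triglycerides and ALT, alongside BMI and blood pressure, as outcomes "assessed at baseline and immediately following the end of the 6 month intervention". For adjustment it says that "covariates will be participants' age, gender, and presence of existing medical conditions". The summary at the front of the document gives the same covariates. Neither place mentions the age of the baseline lab or the time between draws.

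For controls, procedures are "limited to data abstraction from the CHLA KIDS electronic medical record". No window is stated for their baseline or follow-up labs.

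**The concern.** The analysis describes a change over a 6-month intervention, but the collection rule allows the first measurement to be taken well before the intervention starts. Whatever happens to A1C, triglycerides or ALT between the old draw and the first session is then part of the measured change and is credited to the telehealth programme.

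That earlier change could have several sources. It could be ordinary drift. It could be regression toward the mean, if the old result was unusually high. It could also be change under the comparator's own care, because the Inclusion Criteria say: "Youth age 14-18 who meet criteria for or are currently enrolled in the Empower weight management clinic will be included". Baselines would also be of mixed origin, with outside results for some participants and study-unit draws for others.

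At stake is what the three lab comparisons can show. As planned, the intervals differ between participants, are partly pre-treatment, and are not known to be alike in the two arms.

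**Working it through.** The plan gives no figure for the lab interval, so there is none to reproduce. The check is date arithmetic.

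**Inputs from the document**
- L, the age of the baseline lab at the start of participation: 0 to 6 months (the three places cited above).
- Follow-up draw: 6 months after the start, assuming that the visit is on time.

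**Formulas**
- Draw-to-draw interval = L + 6 months.
- Pre-treatment share = L / (L + 6).

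| L (months) | Interval (months) | Pre-treatment share |
|---|---|---|
| 0 | 6 | 0% |
| 1 | 7 | 14% |
| 2 | 8 | 25% |
| 3 | 9 | 33% |
| 4 | 10 | 40% |
| 5 | 11 | 45% |
| 6 | 12 | 50% |

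The possible interval is therefore 6 to 12 months. A late final visit would lengthen it further.

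**Illustration under assumptions.** The document does not say how many participants use prior labs or how old those labs are. Suppose that prior labs are spread evenly over 0 to 6 months, so that their mean age is 3 months.
- All use prior labs: mean interval = 6 + 3 = 9 months. Mean individual pre-treatment share = (1/6) × the integral of L/(L + 6) from 0 to 6 = 1 − ln 2 = 0.307, about 31%.
- Half use prior labs: mean interval = 6 + 0.5 × 3 = 7.5 months. Mean share = 0.5 × 0.307, about 15%.
- None use prior labs: 6 months and 0%.

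Dividing mean lag by mean interval instead gives 3/9 = 33% and 1.5/7.5 = 20%. These are ratios of means, and they are somewhat larger than the average participant's own share.

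**Effect on the estimate.** If a lab drifts by d units per month before the start, a telehealth participant's measured change contains an extra d × L, at most 6d in size. With the same drift in both arms and equal follow-up timing, the error in the difference between arms is d × (mean L in telehealth − mean L in controls). The second mean is not defined anywhere in the document, and d is not given, so neither the sign nor the size can be computed.

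**The case against.** The strongest reply is that bias between arms needs a difference between arms. Controls are Empower clinic patients, and the Schedule of Measurements describes primary-care labs arriving in Empower referral packets. Controls may therefore also have baseline labs that predate their first clinic visit, with a similar lag, and the errors could partly or wholly cancel. This stands. A reader might infer that the lab comparison is biased in favour of telehealth, but the document does not support that. It does not show that the lags are equal either, because no control lab window is stated.

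A reader might also infer that regression to the mean is built in because an abnormal lab prompted referral. Some qualifying conditions, such as hyperlipidemia, pre-diabetes and NAFLD, make this plausible. But BMI above the 99th percentile is enough by itself, other listed conditions are not defined by these three labs, recruitment extends to settings such as the Emergency Department, and item 5 accepts results from any clinical care. Regression to the mean is possible but not established.

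Nor is any particular pre-treatment share a property of the plan. The illustrative percentages depend on an unknown proportion of participants using prior labs, and fall toward 0% if few do.

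Finally, efficacy is the tertiary aim of a pilot sized on practical grounds, and reusing recent labs spares participants a venipuncture. Both points limit how serious this is. Neither makes the lab change a 6-month change.

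**Conclusion.** The concern holds as a mismatch between how lab baselines are collected and how lab change is analysed. With an on-time final visit, the telehealth interval runs from 6 to 12 months, and up to half of it can precede treatment. The between-arm comparisons of A1C, triglycerides and ALT may be biased, in an unknown direction and by an unknown amount. The document gives no lab trend, no distribution of lab ages and no control lab window from which to work these out.

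The scope is limited to the lab outcomes. Weight and other anthropometrics, and blood pressure, are recorded at the in-person baseline visit and are not affected, provided that the analysis uses those values and not the ones that the data list also allows to be abstracted from referral packets or the medical record.

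This is a worthwhile, inexpensive improvement to a tertiary-aim analysis, not a flaw that undermines the pilot.

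**What to change.** No new blood draws are needed.

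1. Record the draw date of every baseline and follow-up lab in both arms. The case report form list names the date of the study visit but not of the lab, so some dates may have to be retrieved from source records. This should be done before the code key is destroyed at study completion.
2. Report, by arm, the distribution of the lag from baseline draw to start (first session or first clinic visit) and of the interval between draws. State which outside labs are accepted: the Schedule of Measurements refers to the referring physician's labs, item 5 to any clinical care.
3. Add one timing covariate to the lab regressions: months from baseline draw to start. Do not add the draw-to-draw interval as well. In the telehealth arm it equals the lag plus about 6, so the two are nearly collinear, and about 30 participants cannot separate them.
4. Run a sensitivity analysis limited to participants whose baseline draw was at the study unit or close to the start, for example within 1 month, and apply the same window to controls.
5. Do not describe the lab results as 6-month changes without these steps.

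The cost is date retrieval, one covariate and one extra run. The restricted analysis may be small. With labs spread evenly over 6 months, one in six falls within a 1-month window. If all 32 telehealth participants used prior labs, 32/6 leaves about 5. If half did, 16 + 16/6 leaves about 19. Both counts are before attrition. The covariate also does not fully remove regression to the mean, and it does not correct for differing follow-up timing among controls, which is why the intervals should be reported too.

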This is a pilot study that aims to compare treatment for obesity in adolescents delivered via a group telehealth model with treatment provided via our traditional in-clinic Empower weight management program, in order to assess feasibility, cost-effectiveness, and efficacy of group telehealth. We will assess efficacy by measuring: (1) Changes in BMI, blood pressure, and relevant laboratory values (2) Quality of life scores (3) Self-efficacy scores (4) Patient satisfaction. Subject recruitment and study design: Patients that have been referred to Empower and the KidsNFitness program will be eligible, as well as CHLA patients seen in a multitude of environments, including outpatient clinics, the Emergency Department, the inpatient setting seen by Physical Therapy, Occupational Therapy, and Clinical Nutrition. In order to be recruited to the intervention group, participants must be between 14 and 18 years of age; informed consent will be obtained. After obtaining their consent, intervention group participants will be assigned to the intervention telehealth group (final total n=32). We plan to run two consecutive 6-month cohorts. Each cohort will consist of two telehealth groups of 6-8 participants each (total 12-16). We plan to over-enroll each group to account for expected attrition; we will enroll a minimum of 6 and maximum of 8 participants in each of the two telehealth groups, for a total of approximately 30 participants (final total n=32) between the two 6-month cohorts. Parents will be contacted on a weekly basis to update them about their child's session attendance, the general content of the sessions, and to remind them to prompt their child to log on to their twice monthly telehealth sessions. We will ask for their preferred mode of contact (text message, email, and/or phone) and use all preferred methods to contact them. Intervention group subjects will be enrolled into a group telehealth program, in which twice monthly sessions will be held using a HIPAA compliant web-based platform, for 6 months.

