The intervention group will be asked to come in for in-person research visits at 0, 3 and 6 months for collection of weight, blood pressure, and other anthropometric measures; they will be asked to complete baseline, 3 month, and 6 month questionnaires regarding quality of life, self-efficacy, diet, and physical activity habits; an additional survey regarding satisfaction with treatment will be administered at end of the 6 month study period, and repeat bloodwork will be obtained at that time.

For the control group, we will use retrospective data for all eligible patients from our Empower clinic whose first clinic visit was between January 2015 and June 30, 2019. The end point for data collection will be no later than December 31, 2019. Those who are matched to the intervention group for age, gender, and severity of obesity; we will request a waiver of consent for this group.

Statistics and data analysis plans: The target recruitment of approximately 206 subjects (30 intervention and 176 control) was arrived at based on practicality and feasibility for a pilot study, and modified per recommendations of our current biostatistician, based on the limited data available upon chart review for many of the clinic control subjects. For evaluation of changes in the continuous outcomes, BMI, blood pressure, and hemoglobin A1C, triglyceride level, and ALT, assessed at baseline and immediately following the end of the 6 month intervention, we

will utilize regression analyses, which will allow us to compare the magnitude of change between the telehealth intervention and the comparison group, taking into account both change from baseline to follow-up time points as well as relevant baseline covariates. For these analyses covariates will be participants' age, gender, and presence of existing medical conditions (e.g. diabetes; rheumatologic conditions) that could affect weight loss.

Background

Prior Literature

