EMPOWER is a multi-disciplinary, team-based clinic model, involving physicians, psychologists, registered dietitians (RDs), and physical therapists (PTs) providing tertiary care management of obesity. Data from the first two years of EMPOWER show that patients with four or more visits (n=109) experienced a decrease in average BMI z-score (-0.09SD). This, though modest, is promising; however, both cost and patient retention present significant challenges to EMPOWER and other tertiary care pediatric obesity programs and may be barriers to further progress. Much administrative personnel time is consumed in working with insurers in order to authorize visits, and nevertheless, this type of hospital-based care is poorly reimbursed. Getting to CHLA is often a major challenge for our patients, due to the large urban sprawl of Los Angeles, traffic, limited and expensive parking, and poor public transportation. Frequent visits result in missed work and school days, a burden to families. Our adolescent patients face even greater challenges, as they they are in the process of learning to manage their own health and balance the emotional and social changes required in the transition to adulthood, with family and parental expectations and limitations.

Rationale for this Study

Telehealth technology presents an innovative, cost-effective, and often highly engaging alternative to in-person visits, which bypasses many of the logistical difficulties of getting to CHLA. Moreover, adolescents today are highly attuned to, and aligned with, digital and mobile technologies, and are natural consumers of media in this format. There is strong evidence from numerous published studies that telehealth can be an effective tool for chronic disease management (1,2, 3). Additionally, many youth with obesity are significantly socially isolated, and our current individual patient-provider model does not effectively address this isolation in the way we expect a group session will; various published studies of group treatment have demonstrated inter-participant support and positive effects of social interaction (4, 5, 6).

While our current model leads to successful weight management in many of our patients, success is often modest, as mentioned above; and for some of our patients, it simply does not work. With this proposal, we wish to pilot a group telehealth model targeted at adolescents with obesity.

Citations:

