
randomized controlled trial examining peer support and behavioral weight loss treatment. Journal of Adolescence. 44:117-123.

Study Objective

Primary Aim -

To pilot a new care delivery model for adolescent patients with obesity, using group telehealth visits

Secondary Aim -

To assess the feasibility of using telehealth with adolescent patients

Tertiary Aim -

To test the efficacy of group appointments using telehealth

Rationale for the Selection of Outcome Measures

- 1. Use of shared medical appointments via telehealth is a feasible, cost-effective care delivery model for adolescents being treated for obesity.
- 2. The efficacy of this model will be comparable to, or better than, standard multidisciplinary in-person visits.
- 3. Attendance to telehealth visits will be better than attendance to standard in-person visits, as measured by no-show rates and same-day reschedules

Study Design

Overview Design Summary

There will be two cohorts for this study, each lasting 6 months. Each cohort will consist of an intervention arm of 12 subjects. We will recruit a minimum of 12 subjects, up to a maximum of 17 subjects in the first cohort and a maximum of 15 in the second cohort, this over-recruitment will attempt to account for possible attrition from the groups.

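### The planned regression ignores the four telehealth groups; with similar arm variances and any positive within-group correlation, its efficacy intervals are somewhat too narrow

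*Combined protocol and SAP*

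**What the plan says.** The opening synopsis plans two consecutive six-month cohorts: "Each cohort will consist of two telehealth groups of 6-8 participants each (total 12-16". That makes four groups. It also says "We plan to over-enroll each group to account for expected attrition". Overview Design Summary describes the size differently ("Each cohort will consist of an intervention arm of 12 subjects", with maxima of 17 and 15). Under Intervention Visits, each group meets for 60 minutes twice a month for six months.

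Controls are retrospective EMPOWER patients. Rationale for this Study contrasts the two kinds of care: "our current individual patient-provider model does not effectively address this isolation in the way we expect a group session will".

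For BMI, blood pressure, haemoglobin A1C, triglycerides and ALT, the Statistical Plan says "we will utilize regression methods, which will allow us to compare the magnitude of change between the telehealth intervention and the comparison group". The covariates, given there and in the synopsis, are "age, gender, and presence of existing medical conditions (e.g. diabetes; rheumatologic conditions) that could affect weight loss". Neither place mentions telehealth group, cohort, an ICC, a robust standard error or a random effect.

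The third aim under Study Objective is "To test the efficacy of group appointments using telehealth".

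**The concern.** Members of a telehealth group share facilitators, sessions and each other's company for six months, and the protocol's rationale relies on that interaction having an effect. Their changes in BMI and other outcomes may therefore be correlated. Controls have no matching structure, so the correlation sits in one arm only.

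A regression with only individual-level covariates takes every participant as independent and, by default, assumes one residual variance for both arms. With positive correlation and similar variances it overstates the information in the telehealth arm, and its interval for the difference is too narrow. The large control group does not dilute this, because the small telehealth arm supplies most of the variance of the difference. At stake is whether the reported precision can support the protocol's hypothesis that telehealth is at least comparable with in-person care.

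**Working it through.** **Inputs from the documents.** There are 2 × 2 = 4 telehealth groups of 6 to 8. The Statistical Plan targets 32 telehealth participants and 176 controls. The head count agrees: 4 × 8 = 32, and 17 + 15 = 32. The target is justified by feasibility, so there is no power calculation to reproduce.

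**Assumptions, none in the documents.** These are the residual ICC of the change after covariate adjustment (0.02, 0.05, 0.10), the telehealth/control variance ratio R, the evaluable numbers, and a nominal 95% interval. The plan names no interval or test.

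**Formulas.** Let m be the evaluable number per group, n = 4m, C the number of controls, and the control variance 1.

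- Design effect: DE = 1 + (m − 1) × ICC
- True SE = √(R × DE/n + 1/C)
- Naive SE, pooled variance = √(sp × (1/n + 1/C)), with sp = ((n − 1)R + (C − 1))/(n + C − 2)
- Naive SE, arm-specific variances = √(R/n + 1/C)
- Miss rate = 2 × (1 − Φ(1.96 × naive SE/true SE))

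**Telehealth share of the variance** (R = 1, m = 6). With 176 controls it is (1/24)/(1/24 + 1/176) = 88%. With 60 controls it is (1/24)/(1/24 + 1/60) = 71%.

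**Worked case** (R = 1, m = 6, C = 176, ICC 0.05). DE = 1 + 5 × 0.05 = 1.25. True SE = √(1.25/24 + 1/176) = 0.2403. Naive SE = √(1/24 + 1/176) = 0.2176. The ratio true/naive is 1.105, and the miss rate is 7.6%.

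**Miss rates, R = 1**

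| Evaluable per group, controls | ICC 0 | 0.02 | 0.05 | 0.10 |
|---|---|---|---|---|
| 4, 176 | 5.0% | 5.6% | 6.6% | 8.3% |
| 5, 176 | 5.0% | 5.8% | 7.1% | 9.3% |
| 6, 176 | 5.0% | 6.0% | 7.6% | 10.2% |
| 8, 176 (no dropout) | 5.0% | 6.4% | 8.5% | 12.0% |
| 6, 60 | 5.0% | 5.8% | 7.1% | 9.2% |

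**Dependence on R** (m = 6, C = 176)

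| R | Method | ICC 0 | 0.02 | 0.05 | 0.10 |
|---|---|---|---|---|---|
| 0.7 | pooled | 2.5% | 3.1% | 4.1% | 6.0% |
| 1.3 | pooled | 7.6% | 9.0% | 10.9% | 14.1% |
| 0.7 | arm-specific | 5.0% | 6.0% | 7.5% | 10.0% |
| 1.3 | arm-specific | 5.0% | 6.1% | 7.7% | 10.4% |

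At R = 0.7 the pooled interval reaches a 5% miss rate at DE = 1.372, which is ICC = 0.372/5 = 0.074. Below that it is not too narrow. With arm-specific variances R hardly matters, and the clustering error is what remains.

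**Simulation check** (regression with four baseline covariates, m = 6, C = 176, ICC 0.05, 20,000 runs). For R = 0.7 / 1.0 / 1.3, ordinary least squares missed 3.9% / 7.4% / 11.0%. Arm-specific variances missed 7.2% / 7.5% / 7.9%. Arm-specific variances with the telehealth variance inflated at the true ICC missed 4.8% / 5.0% / 5.4%.

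**Can four groups estimate the ICC?** The chance that the analysis-of-variance estimate of between-group variance is zero or negative, for m from 4 to 8, is 53–54% at ICC 0.02, 44–50% at 0.05 and 33–43% at 0.10.

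**The case against.** The case against has five parts.

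- **Direction and size rest on unknowns.** No ICC or standard deviation is given, and unequal variances are plausible. Telehealth outcomes come from scheduled visits at 0, 3 and 6 months, while for controls the synopsis gives only a latest date: "The end point for data collection will be no later than December 31, 2019". If telehealth variance is smaller, pooled intervals may be about right or too wide. This stands, and it is why the conclusion is conditional.
- **The regression type is open.** A mixed model is also a regression, and the plan commits to no error structure. True, but none is specified, and the listed terms do not include group.
- **Efficacy is a minor aim.** Feasibility comes first, and bias from unmatched historical controls is a larger threat than a standard error 4–20% too small. This stands and sets the severity.
- **The correction needs an ICC nobody knows.** With arm-specific variances, R = 1 and 6 per group, assuming 0.02 when the truth is 0.10 still misses 8.8%. Assuming 0.10 when the truth is 0.02 misses 2.4%. This also stands, so the remedy is a table over a range and not a single corrected interval.
- **Group membership is probably recoverable from session attendance forms.** Likely so. Recording it as a variable removes the doubt.

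**Conclusion.** The concern holds as a minor point of precision. As listed, the regression treats members of four shared-session groups as independent. With equal arm variances, 6 evaluable per group and 176 controls, the standard error is too small by a factor of 1.04, 1.10 or 1.20 at ICC 0.02, 0.05 or 0.10. Attrition to 4 or 5 per group, or fewer evaluable controls, makes the effect smaller; full retention of 8 per group makes it larger.

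The size depends wholly on the assumed ICC, and the direction under a pooled variance also depends on R. Confidence is medium for that reason. Nothing here bears on bias from the non-randomised control group.

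**What to change.** 1. Record telehealth group as a variable in the analysis dataset before the code keys are destroyed (Study Monitoring, Auditing, and Inspecting). It is not now a listed data item.
2. Estimate each adjusted between-arm difference with a separate residual variance per arm. This removes the dependence on R, so that the clustering allowance does what it is meant to do.
3. Add one sensitivity table that multiplies the telehealth-arm variance by 1 + (m − 1) × ICC at ICC 0.02, 0.05 and 0.10, leaving controls uninflated. Use evaluable group sizes; if they are unequal, take m as the sum of squared sizes divided by the sum of sizes.
4. Name clustering as a limitation and present the efficacy comparison as exploratory.

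A partially nested mixed model (random intercept for group in the telehealth arm only, small-sample degrees of freedom) is optional support. If used, the report should say that a zero variance estimate from four groups is common and is not evidence of no clustering.

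**Cost.** A few SAP sentences, one variable and one small table. Intervals in the table widen by about 4%, 10% and 20% (6 per group, 176 controls, R = 1). Those figures treat the ICC as known; estimating it from four groups, with about 4 degrees of freedom, would give intervals about 1.4 to 1.9 times the naive width over ICC 0.01 to 0.10. The table is conservative if the assumed ICC is too high: assuming 0.10 when the truth is 0 gives a miss rate of 1.3–1.9% with 176 controls and 1.8–2.2% with 60, for groups of 8 down to 6. For groups of 5 down to 4 the rates are 2.2–2.7% and 2.5–2.9%.
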